4.3.2 Discontinue the study product

Patients who experience > Grade 2 skin allergic reaction or > Grade 2 systemic allergic reaction related to the product or placebo must not receive any further TWB-

103 or placebo treatment. If a patient should develop infection at DSW site before Day 10, he/she will stop the TWB-103 or placebo application at the investigator's discretion. Patients with the aforementioned conditions, before or at Visit 8, should finish the scheduled assessments (except that application of TWB-103/placebo is stopped; that the application and dispensation of Tegaderm™ will be at the investigator's discretion; and that the return of Tegaderm™ will be asked if applicable). Patients with allergic reaction or infection may receive appropriate treatments at the PI's discretion, will be monitored throughout the healing process (including the recovery from allergic reaction or infection, and the complete closure of DSW) and will continue the remaining visits (application of TWB-103 or placebo will be stopped if planned originally). In these cases of TWB-103/placebo discontinuation, wound assessments performed after onset of allergic reaction or infection will be excluded from statistical analysis.

4.3.3 Withdraw from the study

Patients may be withdrawn from the study voluntarily or at the investigator's discretion. Refer to Section 3.4 for details.

4.3.4 Unscheduled visits

Unscheduled visits can be requested when patients require the investigator's medical attention, e.g. the reopen of DSW but self-care is insufficient, infection, or allergic reaction. Patients should finish the assessments of Day 14 (except that the completion of hemogram and serum biochemistry as well as the application and dispensation of Tegaderm™ will be at the investigator's discretion; and that the return of Tegaderm™ is not required) during the unscheduled visit. Patients will resume the original planned visits and/or come in additional unscheduled visits at the

investigator's discretion. The option to choose Vaseline Gauze or Non-Stick Gauze such as silastic foam dressings only can be selected on or after Day 14.

5. TRIAL MATERIALS

5.1 Trial Product (s)

TWB-103 is supplied as a two-component therapeutics consisting of one vial of living allogeneic fibroblasts and one vial of gelatin-based hydrogel. The two components are stored separately as the cells need to stay frozen in a -80°C freezer (with temperature not higher than -70°C) and the hydrogel will require a proper storage in a 4°C refrigerator (with temperature at 2~6°C). The cell vial and placebo vial can be stored approximately up to six months after receiving. The expiration date of IP is printed on the label attached to the package of IP as well as the data sheet companying with IP.

5.2 Dosage and Administration

Patients who meet all eligibility requirements for entry into the study will be randomized into one of the treatment group or control group in 1:1 ratio as shown below:

Treatment Group:

TWB-103 add-on Tegaderm™ till 100% re-epithelialization or up to 10 days, whichever comes first, followed by Tegaderm™ alone application from Day 10 to Day 14 if failing to achieve 100% re-epithelialization by Day 10. If 100% re-epithelialization is not observed on Day 14 (the end of treatment), patients will have application of Tegaderm™ up to Day 28.

Control Group:

Placebo+Tegaderm™ till 100% re-epithelialization or up to 10 days, whichever comes first, followed by Tegaderm™ alone application from Day 10 to Day 14 if failing to achieve 100% re-epithelialization by Day 10. If 100% re-epithelialization is not

observed on Day 14 (the end of treatment), patients will have application of TegadermTM up to Day 28.

Note:

1. TegadermTM will be renewed at each visit between Visit 3 (Day 3) to Visit 7 (Day 28) if 100% re-epithelialization is not observed. Whenever TegadermTM falls off from DSW site, new TegadermTM should be applied immediately. If necessary, drainage is allowed, but re-application of TWB-103 or placebo is not necessary in this case.
2. If the first 100% re-epithelialization is observed on Day 28, patients will be scheduled Day 42 follow-up and dispensed with TegadermTM.
3. If the first 100% re-epithelialization is not observed on Day 28, patients will receive the application of TegadermTM on site for protection of wound site and/or have other appropriate treatment at the investigator's discretion. The DSWs will be followed till 100% re-epithelialization.
4. To prevent the itchiness and skin reaction caused by the long-term usage of TegadermTM, Vaseline Gauze or Non-Stick Gauze such as silastic foam dressings can be used on and after Day 14 at the investigator's discretion.

After the creation of DSW (Day 0), the wound site will be covered with gauze containing epinephrine solution (1:100000) for a few minutes and then TWB-103+TegadermTM or placebo+TegadermTM will be applied to DSW site immediately after. Bipolar electrocautery can be used to stop bleeding in some spots if bleeding continues after applying epinephrine and compression for 15 minutes. Dressing will be changed every 3~4 days (on Day 3, 7, and 10) following the procedure stated below.

- (1) Remove the TegadermTM. The wound is properly cleaned by gentle wiping with gauze pad or cotton swab wetted with normal saline or by rinsing the wound with normal saline. The wound is then touched with dry gauze pad or cotton swab to remove excessive fluid or moisture.
- (2) Perform wound assessment.

- (3) Thaw TWB-102 Cells (the treatment group) or freezing solution (control group) at 37°C water bath for 60~80 seconds.
- (4) Taking 0.4 mL cells (the treatment group) or freezing solution (control group) mixed with 4.6 ml gel hydrogel (pre-melted 37°C water bath for ~20 minutes) in one syringe.
- (5) The final mixture will be applied to the target wounds (0.05 mL mixture/cm² wound).
- (6) Cover the wound area with Tegaderm™.

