Study Product, Dose, Route, Regimen	TWB-103, allogeneic human fibroblasts + gelatin-based hydrogel, applied 2 to 3 times till 100% re-epithelialization or up to 10 days (around once every 3 days); a matching placebo, freezing solution with gelatin-based hydrogel, is used as the control and applied to patients in the same duration and dosing frequency as TWB-103.
Duration of Treatment	During the planned treatment period (14 days), each patient will receive TWB-103+Tegaderm™ or placebo+Tegaderm™ for up to 10 days or to the day of 100% re-epithelialization, whichever comes first, followed by Tegaderm™ alone application from Day 10 to Day 14 if failing to achieve 100% re-epithelialization by Day 10.
Study Visits	
Patients will be scheduled to attend the following visits:
 
1. Screening (within 2 weeks prior to DSW creation)2. Day 0 (treatment begins)3. Day 3 (\pm 1 day)4. Day 7 (\pm 1 day)5. Day 10 (\pm 1 day)6. Day 14 (\pm 2 days, end of treatment)7. Day 28 (\pm 3 days, Follow-up)8. Day 42 (\pm 3 days, Follow-up)

9. 90 ± 14 days after Visit 7 or Visit 8 (Follow-up)

10. 180 ± 14 days after Visit 7 or Visit 8 (Follow-up)

11. 270 ± 14 days after Visit 7 or Visit 8 (Follow-up)

12. 360 ± 14 days after Visit 7 or Visit 8 (Follow-up)

Note: (1) For patients with complete wound closure by Day 14, the confirmation of wound closure will be assessed on Day 28.

(2) Day 42 follow-up is only scheduled when the wound closure is not completed by Day 14 but is observed on Day 28. The wound closure will be re-confirmed on Day 42.

(3) If no Visit 8, Visit 9~12 should be scheduled following Visit 7.

(4) In case patients achieve 100% re-epithelialization before or at Day 10, patients will finish up the assessments on the day with 100% re-epithelialization. This day of 100% re-epithelialization will be the end of treatment and the remaining scheduled treatment visits, if applicable, will be dismissed.

Patient Assignment Patients who meet all eligibility requirements for entry into the study will be randomized into one of the treatment group or control group in 1:1 ratio as shown below:

Treatment Group:

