5.5 Product Accountability

All patients are administered IP or control material at the clinical site (Visit 2~4). All of the unused IP and control material will be asked to be destroyed on site or returned from the clinical site to the sponsor. Each IP and control material shipped, used, and

returned will be recorded with a date in order to keep track of the IP and control material in precise details.

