5.6 Assessment of Compliance

The IP or control material will be administered at the study site at scheduled visits (Visit 2~4). Patient compliance should not be a severe issue. However, the study monitor will assure the patient's compliance with the study protocol.

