6.10 Investigational Product

Investigational drugs will be administered to eligible patients at Visit 2~4, starting with the Administration visit (Day 0). Drug accountability and inventory will be recorded in the CRFs and the relevant study log.

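### The step list in Section 5.2 includes product application on Day 10 with no exception, which conflicts with Section 5.2's own arm text and with the visit schedule (four applications against three for a patient unhealed at Day 10)

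*Combined protocol and SAP*

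**What the plan says.** Section 5.2 (Dosage and Administration) covers the Day 0 application and then says: "Dressing will be changed every 3~4 days (on Day 3, 7, and 10) following the procedure stated below". Six steps follow: remove the dressing and clean the wound; assess it; thaw the cells or freezing solution; mix with hydrogel; apply the mixture; cover with Tegaderm. Step 5 reads: "The final mixture will be applied to the target wounds (0.05 mL mixture/cm² wound" (the bracket closes there). No step is limited to particular days.

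Earlier in Section 5.2, the descriptions of both arms give product up to 10 days or until healing, then Tegaderm "alone application from Day 10 to Day 14 if failing to achieve 100% re-epithelialization by Day 10".

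Other places that fix the number or the days of application:

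- Protocol Summary, study product row: "applied 2 to 3 times till 100% re-epithelialization or up to 10 days (around once every 3 days").
- Section 5.5: "All patients are administered IP or control material at the clinical site (Visit 2~4"). Sections 5.6 and 6.10 name the same visits.
- Sections 7.3.1 and 7.3.2 (Days 3 and 7) list study medication for an unhealed wound. Section 7.3.3 (Day 10) lists only Tegaderm, for both groups.
- The Schedule of Assessments has three product marks, and its row for Tegaderm applied at the site starts at Day 10.

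Section 10.2.1 makes having been dosed according to plan a condition for the per-protocol set. Sections 3.1 and 10.1 make that set the evaluable population, with a target of 30.

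**The concern.** Section 5.2 is the only place that sets out how the product is prepared and applied, so staff are likely to work from it. It names Day 10 on the same footing as Days 3 and 7, which are product days everywhere else. A site that follows the steps as written and a site that follows the Day 10 visit list would treat the same unhealed patient differently.

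Three things are at stake:

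- **Exposure.** The study is described as first-time-in-human (Sections 1.2.1 and 1.2.4) and has no DSMB (Section 10.2.4). The Phase I safety review rests on 3 evaluable patients treated with TWB-103, so a difference in exposure among them would blur it.
- **Evaluability.** If the planned regimen has two readings, a patient unhealed at Day 10 can meet the per-protocol dosing criterion under one and fail it under the other. The count towards 30 then depends on the reading chosen.
- **Pooling.** Section 10.2.1 justifies combining Phase I and Phase II data by the identity of the dosing regimen in both.

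**Working it through.** No power or sample-size formula applies. The check is a count of application days, followed by the implied volume.

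**Inputs.** Visits 2, 3, 4 and 5 are nominally Days 0, 3, 7 and 10 (Protocol Summary, study visits). Product stops once the wound is seen to be healed (schedule footnote 5). The amount is 0.05 mL per cm² (Section 5.2, step 5). Eligible wounds measure 15 to 100 cm² (Section 3.2).

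**Rule.** Number of applications = number of listed application days that fall before the visit at which healing is first seen.

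| Healing first seen at | Visits 2 to 4 (Days 0, 3, 7) | Section 5.2 step list (Days 0, 3, 7, 10) |
|---|---|---|
| Day 7 | 2 | 2 |
| Day 10 | 3 | 3 |
| After Day 10 | 3 | 4 |

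**The plan's own figure.** The synopsis states 2 to 3 applications. Visits 2 to 4 reproduce this: 2 if healed at Day 7, otherwise 3. The step list read literally does not, because its maximum is 4. (A wound healed at Day 3 would have had 1 application under either reading, but Section 1.1 expects healing in 7 to 21 days.)

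**Size of the difference.** 4 − 3 = 1 application, and 4/3 − 1 = 0.33, so one third more applications. It arises only in patients unhealed at Day 10.

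**Volume**, assuming the full original wound area is dosed each time:

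- 100 cm²: 0.05 × 100 = 5 mL per application; 3 × 5 = 15 mL against 4 × 5 = 20 mL.
- 15 cm²: 0.05 × 15 = 0.75 mL per application; 3 × 0.75 = 2.25 mL against 4 × 0.75 = 3.0 mL.

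If only the area still open is dosed, the extra volume on Day 10 is smaller. The count of 3 against 4 does not change.

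**Whether the arm text settles it.** Tegaderm alone from Day 10 points away from product on that day. The companion phrase, that product is given up to 10 days, does not say whether Day 10 itself is included, and the Day 10 visit has a window of ±1 day. So the conflict lies within Section 5.2 as well as between it and other sections.

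**The case against.** The strongest reply is that no rival regimen exists. The Section 5.2 arm text comes before the step list and gives Tegaderm alone from Day 10. The sentence that introduces the steps is about changing dressings. The steps also make no exception for a wound found healed at step 2, yet nobody would apply product to a closed wound, because the arm text governs. The Day 10 visit list, the schedule and Sections 5.5, 5.6 and 6.10 all speak against a fourth application.

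Much of this stands. A careful site may well skip steps 3 to 5 on Day 10, so 3 against 4 is what the text permits, not a forecast of what sites will do. But the step list names Day 10 expressly and carries no limit, so the reader must resolve the conflict without help.

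Three stronger readings are tempting, and the documents do not support them:

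- *Section 5.2 stands alone against every other section.* Part of the conflict is inside Section 5.2, and Sections 4 and 4.1 name no application visits.
- *A large share of patients would be affected.* The 7 to 21 days in Section 1.1 is a range that depends on graft thickness. No distribution of healing times is given.
- *The primary efficacy comparison would be biased.* Section 10.2.1 draws the conclusion from the ITT population, randomization is stratified by site (Section 4.2), and the step list is the same for both arms, so a site's misreading would apply to both. What could vary between sites is the regimen being compared.

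**Conclusion.** The contradiction holds as an internal inconsistency, not as a fault in the choice of design. For a patient unhealed at Day 10 the protocol supports either three or four applications. Everyone healed by Day 10 gets the same number under both readings. The result rests on nominal visit days and on a literal reading of the step list; how many patients it concerns cannot be derived from the documents.

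The consequences are ambiguous exposure in a first-in-human study and an ambiguous per-protocol criterion, and with it the evaluable count. The primary efficacy conclusion is less exposed because it is drawn from the ITT population. It should be corrected. More places in the text give three applications than four, but this review does not say which schedule is right; that is for the sponsor to confirm.

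**What to change.** Reconcile the Section 5.2 step list with the Section 5.2 arm descriptions, the synopsis, Sections 5.5, 5.6, 6.10 and 7.3.3 and the Schedule of Assessments, so that one set of application days, confirmed by the sponsor, appears throughout. Split the step list in two: the steps for every dressing change, and the preparation and application steps with the visits at which they apply. State whether the 10-day limit includes the Day 10 visit. Then let the per-protocol dosing criterion in Section 10.2.1 refer to that set of days.

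The cost is protocol wording, with whatever IRB approval Section 11.2 requires. Visits, sample size and analysis methods do not change. For patients already treated, Section 5.5 requires product use to be recorded with a date, so any application on Day 10 can be identified.

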5.3 Package and Labeling

The investigational product (IP) will be packaged in vials for each administration. All vials will be labeled for study number, vial identifier, prescription instructions, the investigator's name, storage conditions, expiry date, and the descriptions of "Clinical trial use only" and "Keep out of the reach of children".

5.4 Storage and Drug Accountability

The IP shipping is to be arranged by the Sponsor to the study site and to be handled by the investigator or the designated pharmacist for management and administration. The two components are stored separately as the cells need to stay frozen in a -80°C freezer and the hydrogel will require a proper storage at 2~6°C. TWB-103/placebo can be stored up to six months before clinical application.

5.5 Product Accountability

All patients are administered IP or control material at the clinical site (Visit 2~4). All of the unused IP and control material will be asked to be destroyed on site or returned from the clinical site to the sponsor. Each IP and control material shipped, used, and

returned will be recorded with a date in order to keep track of the IP and control material in precise details.

5.6 Assessment of Compliance

The IP or control material will be administered at the study site at scheduled visits (Visit 2~4). Patient compliance should not be a severe issue. However, the study monitor will assure the patient's compliance with the study protocol.

5.7 Treatment for Investigational Product Overdose

Product overdose will not be of concern as the dosing regimen of TWB-103/placebo in this study is to be administered at the site by site medical staff and believed to be safe. If over dosage should occur, the patient or the person in charge of caring for the patient should contact the investigator as early to determine if any immediate medical treatment is needed. The patient should also be arranged as soon as possible for evaluation before any further IP treatment can be proceeded. This post-overdose visit can be an un-scheduled or a regular study visit. The study monitor appointed by the sponsor should be contacted by the investigator of any over-dose report as soon as being aware of the event. Any unfavorable effects caused by the overdose event must be reported as an AE and even SAE.

5.8 Other Consideration for Investigational Product

Because nicotine interferes the wound closure, smoking is not allowed from one week prior to Day 0 till Day 14.

6. STUDY ASSESSMENTS

6.1 Informed Consent

All patients must provide signed informed consent at the Screening visit, prior to any study-related procedures. Only the institutional review board (IRB) approved informed consent form can be used.

6.2 Demographics

Demographic data, including age, gender, weight and height information will be obtained at the Screening visit.

6.3 Pregnancy Test and Contraception

Patient with childbearing potential must be confirmed of not being pregnant at the Screening visit. The pregnancy test should be done at the screening visit, which is within 2 weeks prior the DSW creation and the treatment. Both male and female patients should also be informed that defined contraceptive methods must be used from signing informed consent to 30 days after the last dose administration.

Acceptable contraceptive forms include:

- a. Established use of oral, injected or implanted hormonal methods of contraception
- b. Placement of an intrauterine device (IUD) or intrauterine system (IUS)
- c. Barrier methods of contraception: Condom or occlusive cap (diaphragm or cervical/vault caps)

6.4 Eligibility

Eligibility should be thoroughly checked by the investigator at Screening Visit. See Sections 3.2 and 3.3 for detailed eligibility criteria.

6.5 Physical Examinations

The patient will be examined at each scheduled visit by standard physical examination items including general appearance, skin, eyes, ears, nose, throat, head and neck, heart, chest and lungs, abdomen, extremities, lymph nodes, musculoskeletal, neurological, other body systems if applicable for describing the status of the patient's health.

6.6 Medication History

Previous medications are categorized into therapies relevant or not related to cutaneous wound/ulcer at the Screening Visit. The cutaneous wound/ulcer-irrelevant therapy should only be recorded up to 4 weeks before study entry. The cutaneous wound/ulcer therapy (all kinds of modality) should be recorded for at least 3 months prior to Screening Visit.

6.7 Medical History

The general medical history up to 3 months of study entry should be recorded at the Screening Visit. The medical history should include procedural within a 1 year time and major surgical history for the life time base. The history of cutaneous wound/ulcer for the coming DSW creation will be recorded in the "cutaneous wound/ulcer history" part of the CRF, separately. Medical history and cutaneous wound/ulcer history will include date of onset, location, and diagnosis, prior therapies, and current status. The cutaneous wound/ulcer history should be recorded for lifetime of the patient.

6.8 Vital Signs

Patient will be measured of blood pressures, pulse rate and body temperature at all scheduled visits.

6.9 Hematologic and Biochemical Indexes

The hematologic and biochemical indexes will be measured at Visit 1~8. For Visit 2, the hematologic and biochemical tests conducted within 7 days prior to Day 0 are acceptable. The items to be measured include the following:

Hematology: hemoglobin, hematocrit, Red blood cell (RBC), platelet, White blood cell (WBC) with differential counts, Absolute neutrophil count (ANC)

Biochemistry: aspartate transaminase (AST), alanine transaminase (ALT), serum creatinine, blood urea nitrogen (BUN), albumin, total bilirubin, gamma-glutamyl transferase (γ -GT), alkaline phosphatase (Alk-P)

6.10 Investigational Product

Investigational drugs will be administered to eligible patients at Visit 2~4, starting with the Administration visit (Day 0). Drug accountability and inventory will be recorded in the CRFs and the relevant study log.

6.11 Wound assessment

The wound assessment will be measured at all scheduled visits except the Screening Visit.

From Visit 2 (Day 0) to Visit 8 (Day 42), the investigator will determine the end of treatment based on the healing progress. Wound healing will be assessed based on the wound observation by the investigator and an additional evaluator. An additional evaluator who is not aware of the treatment given will evaluate based on photos of the wound. The additional evaluator will receive photos of the wound from CRO and will return the assessment to CRO. A second additional evaluator, who is also blinded, will

be requested when the discrepancy occurs between investigator and the first additional evaluator in the determination of 100% re-epithelialization.

The photos of wound will be taken under the following guidelines.

- (a) Cameras and rulers with the same brand and model will be used throughout the study.
- (b) The study staff who are trained will be in charge of taking photos following the guidelines for each study center.
- (c) Two different photos will be taken for each wound at each visit: one for the calculation of wound healing and the other as the reference of the wound location relative to the body part.
- (d) The wound area shown in the photo specific for calculation purpose, along with the provided ruler, should have sufficient size and quality for evaluation.
- (e) Images will be processed by the software, Image J.
- (f) The investigator and evaluator(s) will select the boundary of said wound in the photo manually and by the wand tool in Image J.
- (g) Calculate the wound size by Image J based on the area selected.
- (h) The healing percentage of wounds will be calculated by the ratio of healing area and original area (Day 0).

Complete wound closure is defined as skin 100% re-epithelialization without drainage or dressing requirements. Wound closure should be re-confirmed on Day 28 when the complete wound closure occurs by Day 14, or on Day 42 in the case that complete wound closure occurs at some point between Day 14 and Day 28.

During the 360 days of follow-up (Visit 9~12), recording of 100% re-epithelialization and the area of target wound are not required. Instead, potential long-term adverse

events will be determined and recorded, including scar assessment (Vancouver Scar Scale and if necessary, additional comments on scar elasticity, scar color and pigmentation), skin texture (relationship to surrounding skin, texture, margins, size and multiplicity), pain assessment (see section 6.12) and any altered sensations.

